### 6.3 Safety Information

(1) Laboratory tests such as complete blood count/liver and kidney function , chest CT/X-ray, electrocardiogram: collected based on actual clinical situations ;

(2) Incidence of adverse events/adverse reactions.

## 7 Safety observation

### 7.1 definition

(1) Adverse Event, AE)

In drug clinical trials, any adverse medical event that occurs after a subject receives a test drug is called an adverse event. Adverse events can manifest as diseases, symptoms, signs or laboratory abnormalities, and adverse events do not necessarily have a causal relationship with the investigational drug.

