	D5 or before discharge: complete blood count, CRP, and chikungunya nucleic acid tests; Follow-up after treatment; telephone follow-up on D7, D14, and D28.
General information and medical history	1. Demographic information: gender, age, height, weight, ethnicity, etc.; 2. Medical history: past medical history, current medical history, epidemiological history and allergy history.
Effectiveness evaluation	

1. Joint Pain and Swelling Relief Rate (DAS44 Score)

2. Change in Rash Severity (Modified EASI Score)

3. Time to Complete Fever Resolution

4. Time to Viral RNA Clearance (RT-PCR Negative)

5. Recovery of Laboratory Markers

6. Time to Symptom Recovery

7. Incidence of Complications

Safety evaluation	Incidence of adverse events/adverse reactions.

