### 5 Observation Cohorts and Treatments

#### 5.1 Treatment Allocation by Cohort

- Chinese Medicine Group: Chinese treatments, which may include herbal formulas (e.g., decoctions, granules) or acupuncture, tailored to their syndrome differentiation (e.g., heat-clearing, detoxifying, or dampness-resolving therapies).;

- Western medicine group: Patients receive only standard Western medical care, which may include antipyretics (e.g., acetaminophen), NSAIDs for pain, and supportive treatments (e.g., hydration);
- Integrated therapy group : receive both Chinese and Western treatments.

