**(2) Serious adverse events Adverse Event, SAE)**

It refers to adverse medical events such as death, life-threatening, permanent or severe disability or loss of function, the need for hospitalization or prolonged hospitalization, congenital abnormalities or birth defects, etc. that occur after the subject receives the investigational drug.

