**(4) Adverse drug reactions drug reaction, ADR )**

In drug clinical trials, harmful or unexpected reactions to the human body caused by the test drugs are called adverse reactions.

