### 7.4 Determination of causal relationship between adverse events and drugs

Technical Guidelines for the Evaluation of the Correlation of Adverse Events in Clinical Trials of Drugs (Trial Implementation)  issued by the CDE , a comprehensive evaluation of the correlation between individual adverse events in clinical trials and the test drugs was conducted based on five evaluation points (whether there is a reasonable time relationship, whether it is consistent with the known drug mechanism, characteristics or known adverse reactions of the drug, destimulation results, restimulation results, and whether other reasonable reasons can be used to explain it). According to different situations, the judgment results are divided into five categories: related, very likely related, possibly related, possibly unrelated, and unrelated. Among them, "related, very likely related, and possibly related" are judged as adverse reactions and included in the calculation of adverse reaction incidence. See Table 1 and Table 2 for details.

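### Adverse reactions are judged against a test drug the protocol never identifies, so the adverse-reaction rate has no common meaning across the three cohorts

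*Protocol*

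**What the plan says.** The Program Summary and section 6.3 name the safety outcome as "Incidence of adverse events/adverse reactions". The definitions behind it all refer to one drug, under several names:

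- Section 7.1(1): "any adverse medical event that occurs after a subject receives a test drug is called an adverse event".
- Section 7.1(2): serious adverse events are those "that occur after the subject receives the investigational drug".
- Section 7.1(4): "harmful or unexpected reactions to the human body caused by the test drugs are called adverse reactions".
- Sections 7.2 and 7.3: the investigator judges relevance to the trial drug.
- Section 7.4: an evaluation of "the correlation between individual adverse events in clinical trials and the test drugs was conducted based on five evaluation points", one of which is "whether other reasonable reasons can be used to explain it". Events in the top three of five categories "are judged as adverse reactions and included in the calculation of adverse reaction incidence".
- Section 7.6.2: a serious event whose causality the investigator has not assessed counts as related to the investigational product.

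Section 5.1 describes the treatments. The Chinese medicine group may have herbal formulas or acupuncture. In the Western group, "Patients receive only standard Western medical care", which may be antipyretics, NSAIDs or supportive measures such as hydration. The integrated group has both. Section 11 says that the study does not interfere with treatment. The only named product, Jingfang Heji, appears in section 9.2 on hospital sampling. It is tied to no cohort and is not called the test drug.

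**The concern.** An adverse-reaction rate can be compared between cohorts only if the same question is asked of each event in each cohort. Here the question is whether the event was caused by the test drug, and the protocol does not say which treatment that is. Each site has to decide for itself.

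Objective 2 includes the safety of Chinese medicine, and section 10 compares categorical indicators between groups by chi-square or Fisher's exact test. A difference in adverse-reaction rates could then reflect how sites read two words rather than how patients fared. Analysis alone cannot repair this, because relatedness is a judgement that the investigator makes and signs (section 7.3). Section 7.4 allows a judgement to be revised, but that means going back to the sites event by event.

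**Working it through.** The protocol states no expected reaction rate and no sample size (section 3.1 takes all patients who can be collected), so it has no figure to reproduce. The check has three parts.

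**1. What the numerator becomes under each reading of *test drug***

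| Reading | Chinese medicine cohort | Western cohort | Integrated cohort |
|---|---|---|---|
| Chinese medicine | defined for herbal formulas; unclear for acupuncture, which is not a drug | zero by construction | only reactions attributed to the Chinese component |
| Jingfang Heji | only patients given that product | zero by construction | only patients given that product |
| Each cohort's own treatment | as in the first row | defined for drugs; unclear for hydration | no rule for which component is judged |

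The numerator differs between the rows, and no section selects one.

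**2. The integrated cohort under Tables 1 and 2 of section 7.4**

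Suppose that relatedness is judged against one component, and that the other component is a reasonable explanation of the event.

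- The top two categories are closed, since both require that there be no other reasonable explanation.
- With positive dechallenge and a fit to the drug's known profile, the event can stay in *May be related*. Table 2 has a column for this combination. The event still counts in the rate.
- Without positive dechallenge, the event can fall to *Probably not relevant* and leave the rate. For an event that fits the known profile, Table 1 asks that the other explanation be more reasonable; for one that does not fit, any reasonable explanation is enough. Special note 4 treats a dechallenge that was not performed or not applicable as lacking, so this route is realistic.

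Some integrated-cohort events, chiefly those without positive dechallenge, could therefore drop out because the other study component explains them.

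**3. How large the artefact could be**

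Assumptions, none of them from the protocol: two cohorts of n patients each, the same true reaction rate in both, and one cohort recorded as zero because of the definition. With k reactions, all in one cohort, two-sided Fisher is

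P = 2 × C(n, k) / C(2n, k) = 2 × product over i = 0 to k−1 of (n − i)/(2n − i).

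| True rate | n per cohort | k | One tail | Two-sided P |
|---|---|---|---|---|
| 2% | 200 | 0.02 × 200 = 4 | 0.0616 | 0.12 |
| 5% | 100 | 0.05 × 100 = 5 | 0.0297 | 0.059 |
| 5% | 200 | 0.05 × 200 = 10 | 0.00087 | 0.0017 |

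Of these three cases, only the last passes the 0.05 level of section 10.

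**The case against.** Four points can be made on the other side.

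- **The all-cause adverse-event rate is largely protected.** Section 7.2 records events from the start of the treatment period to the last visit, without limiting this to a cohort, and the flow chart has an adverse-event row from D1 to D28 for everyone. This stands, although the literal definition in 7.1(1) still conflicts with that window. It does not rescue the adverse-reaction rate, because 7.2 itself asks about relevance to the trial drug.
- **A lenient reading exists.** Sections 7.1(4) and 7.4 use the plural *test drugs*, and section 4.6 speaks of study treatment, so each cohort's own treatment may be meant. This is possible, but no section says so, and it leaves acupuncture and the integrated cohort unresolved. It does mean that a reader who infers that the Western rate must be zero goes too far: that follows only if the test drug is Chinese medicine or Jingfang Heji.
- **Co-treatment does not always lower the count.** A reader might infer that in the integrated cohort the Western drug always counts as another reasonable explanation and so removes the event. It does so only where it plausibly explains that event, and Table 1 keeps some such events in a category that counts.
- **This is template wording.** Unblinding (7.5, 7.6) and an investigator's brochure (7.1(5)) also appear in this open observational study, and sites may well record reactions to NSAIDs whatever the definition says. That explains the text, but the rule is still unfixed.

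**Conclusion.** The point holds in this form: the referent of the causality judgement is not defined, and the adverse-reaction incidence built on it has no common numerator across the cohorts. This follows from the text alone and needs no assumption about rates. It should be corrected, ideally before relatedness is recorded.

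The size is unknown. The P values of 0.12, 0.059 and 0.0017 rest on assumed rates and cohort sizes and on one cohort being recorded as exactly zero. They show that a spurious difference is possible at moderate size, not that it will occur. The documents do not support saying that the Western rate is zero by definition, that every integrated-cohort event is down-graded, or that the comparison of all-cause adverse events is lost.

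**What to change.** - Throughout sections 7.1 to 7.6, replace test, trial or investigational drug (or product) by *any treatment under observation (herbal medicine, acupuncture or Western medicine)*. Where those words stand in instructions on stopping or adjusting treatment or on unblinding (7.5, 7.6), the sponsor must reconcile them with the three cohorts; no clinical rule is proposed here.
- Count adverse events from the start of the observed treatment in every cohort, in line with the section 7.2 window.
- In 7.4, record relatedness separately for each component received. Count an event as an adverse reaction if it is at least possibly related to any component. State that, for this any-component judgement, another study component is not an *other reasonable reason*.
- Report the adverse-reaction rate for any component in all three cohorts, and by component.

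The cost is revised wording, a relatedness entry for each component on the recording form, and slightly more work for sites. Events already judged under the present wording would need to be judged again.

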**Events that meet the definition of adverse events include:**

Exacerbation of a pre-existing chronic or intermittent illness, including an increase in frequency and/or severity of illness;

New diseases detected or diagnosed after administration of the investigational drug, even though they may have existed before the start of the study;

signs, symptoms, or clinical sequelae of suspected drug interactions;

Signs, symptoms, or clinical sequelae of suspected overdose of the investigational drug or co-administered drug (overdose itself is not reported as an adverse event/serious adverse event).

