**Flow chart**

Stage	Screening Period / Baseline	Treatment observation period							Follow-up after treatment (telephone follow-up)		
		Visit 1 D0	Visit 2 D1	Visit 3 D2	Visit 4 D3	Visit 5 D4	Visit 6 D5	Visit X Before discharge	Visit 7 D7	Visit 8 D14	Visit 9 D28
Visit point (D, day)											
Informed consent form	×										
Chikungunya RNA test	×						×	×			
Epidemiological data	×										
General information and medical history	×										
Physical examination, vital signs	×				×		×	×			
Body temperature	×	Patient diary card for body temperature record									
Chikungunya Symptom Scale	×	×	×	×	×	×	×	×	×	×	×
Complication		×	×	×	×	×	×	×	×	×	×
Severe / critical illness		×	×	×	×	×	×	×	×	×	×
Laboratory tests	×						×	×			
Patient diary card collection	×						×	×			
Medication records	×	×	×	×	×	×	×	×			
Adverse Events		×	×	×	×	×	×	×	×	×	×

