#### 3.2 Visit

Screening period/baseline: First visit D0, complete blood count, CRP, chikungunya nucleic acid and liver and kidney function tests

Treatment observation period: D1-D5, daily follow-up, filling in the CRF, collecting the complete blood count, CRP, and Chikungunya fever nucleic acid results on D5/Discharge day.

Follow-up after treatment; telephone follow-up was conducted on D7, D14, and D28.

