## 5.2 Observation period and follow-up

Maximum observation period: 28 days

Visit time:

Screening period/baseline: First visit D0, with lab assessments: complete blood count, CRP, and chikungunya nucleic acid tests;

Treatment observation period: D1-D5, daily follow-up with clinical and lab assessments, D5 or before discharge: complete blood count, CRP, and chikungunya nucleic acid tests;

Follow-up after treatment; telephone follow-up on D7, D14, and D28.

On D0, D5 or before discharge, collect 8 ml of whole blood (anticoagulant tube) for storage.

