#### ■ VAS (Visual Analog Scale) pruritus score

No itching at all 0--1--2--3--4--5--6--7--8--9 — 10 Worst itching point

**(3) Complete fever reduction time: Complete fever reduction is defined as the body temperature dropping to 37.2°C or below after the first dose and maintained for 24 hours or more;**

(4) Nucleic acid negative conversion time;

(5) Time for single symptom to disappear;

(6) Overall symptom disappearance time;

(7) Time for white blood cell count to return to normal: the time from the first dose to the first observation of white blood cell count returning to normal;

(8) Time for platelet count to return to normal: the time from the first dose to the first observation of platelet count returning to normal;

(9) Incidence of Chikungunya-related complications: Proportion of patients with recorded AEs for Chikungunya-related complications (shock, DIC, encephalitis, acute liver injury, acute kidney injury, myocarditis, pericarditis, pneumonia, respiratory failure, rhabdomyolysis, acute pancreatitis) after the start of treatment.

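### The complication incidence in 6.2(9) can count complications present but undetected at entry as post-treatment events, because it uses adverse event records with no at-risk condition or baseline complication entry

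*Protocol*

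**What the plan says.** Section 6.2(9) of the protocol defines the incidence of chikungunya-related complications as "Proportion of patients with recorded AEs for Chikungunya-related complications", names eleven of them, and sets the window as "after the start of treatment". Nothing there restricts the count to patients without the complication at baseline. The Program Summary also lists complication incidence under effectiveness.

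Section 7.1 lists what qualifies as an adverse event. One item is "New diseases detected or diagnosed after administration of the investigational drug, even though they may have existed before the start of the study". Another is "Exacerbation of a pre-existing chronic or intermittent illness, including an increase in frequency and/or severity of illness".

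In the flow chart, the row "Complication" and the row for severe or critical illness are both blank in the Screening/Baseline column.

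The protocol is not consistent about baseline tests. Section 3.2 has "Screening period/baseline: First visit D0, complete blood count, CRP, chikungunya nucleic acid and liver and kidney function tests". Section 5.2 has "First visit D0, with lab assessments: complete blood count, CRP, and chikungunya nucleic acid tests", with no liver or kidney function, and the Program Summary agrees with 5.2. Section 6.3 says that liver and kidney tests, chest imaging and electrocardiogram are "collected based on actual clinical situations".

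**The concern.** The rule in 7.1 dates a disease by when it is detected, which suits safety capture. Section 6.2(9) reuses those records as an effectiveness incidence, where the date that matters is onset. Patients may enter with up to three days of symptoms (section 4.2), so a complication can begin before the first dose and be found after it. Under the stated rules it is then a post-treatment complication.

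Section 4.4 forms the cohorts by what was actually prescribed, so patients may differ in severity at entry. If undetected complications are more common at entry in one cohort, that cohort shows a higher complication rate that treatment did not cause. The confounding methods in 9.1.4 adjust for baseline differences. They do not by themselves remove baseline events from the outcome.

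**Working it through.** The protocol states no complication rate, sample size calculation or power, so there is no figure to reproduce. Two checks apply.

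**1. The counting rule, step by step.** Take a patient whose D0 blood sample shows liver injury, with the result returned after the first dose.

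- Section 7.1: the condition is diagnosed after administration, so it is an adverse event even though it pre-dates treatment.
- Section 6.2(9): acute liver injury is on the list and an adverse event is recorded after treatment began, so the patient enters the numerator.
- Flow chart: no baseline complication entry exists that would mark the patient as not at risk.

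The general definition in 7.1(1) and the recording rule in 7.2 speak of events that occur after dosing or from the start of treatment. The protocol therefore carries two timing rules, onset and detection, and 6.2(9) does not say which one governs.

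**2. Illustration of size, with assumed rates.** Let u be the share of a cohort with a complication that is present but undetected at baseline and found after the first dose. Let i be the true incidence of new complications in the rest. Then

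recorded incidence = u + (1 − u) × i

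share of recorded cases already present at baseline = u / [u + (1 − u) × i]

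| u | i | Recorded incidence | Share present at baseline |
|---|---|---|---|
| 0 | any | i | 0% |
| 0.5% | 1% | 1.5% | 33% |
| 0.5% | 3% | 3.5% | 14% |
| 0.5% | 5% | 5.5% | 9% |
| 2% | 1% | 3.0% | 67% |
| 2% | 3% | 4.9% | 40% |
| 2% | 5% | 6.9% | 29% |

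Between cohorts, take i = 1% in both, so there is no treatment effect:

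- u = 3%: 0.03 + 0.97 × 0.01 = 3.97%
- u = 1%: 0.01 + 0.99 × 0.01 = 1.99%
- ratio: 3.97 / 1.99 = 1.99

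Swapping the two values of u reverses the direction. With equal u and equal i the difference is zero. With equal u and unequal i, the true difference is multiplied by (1 − u), so no difference is created.

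**The case against.** The strongest case against the point has five parts.

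- **The clause in 7.1 is narrow.** It covers disease newly detected after administration. A reader might infer that every complication present at baseline enters the incidence. The text does not support that: a complication already recognised at D0 is not new under this clause. Only undetected ones are at issue.
- **The flow chart is ambiguous.** A reader might infer that complications are not recorded at D0 at all. As extracted, the table has eleven data columns for ten labelled visits, and the complication row has a mark under Visit 1 D0, inside the treatment observation period. Elsewhere the protocol equates baseline with D0, so the layout may be an artefact. What can be said safely is that the baseline column has no complication entry. On either layout, no pre-dose entry is set apart.
- **Other data help.** History, concomitant disease, current illness, physical examination and laboratory tests are collected at baseline (flow chart, 6.1), and 7.2 requires each adverse event's time of occurrence. These allow partial correction, so the problem is not beyond repair in analysis. But 6.2(9) does not use them, and most listed complications, such as pneumonia, myocarditis and pancreatitis, have no named baseline test.
- **Severe disease is excluded (4.3), and cases can be removed later (4.5, 4.7).** Sections 4.1 to 4.3 do not say what counts as severe, though the cited national guidance may. An undiagnosed complication cannot trigger an exclusion at enrolment. Later removal is left to unspecified judgement at data review.
- **A counting rule may belong in a statistical analysis plan, which is not shown.** Such a plan could narrow the numerator. It could not fully recover a baseline status that was never recorded.

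Complication incidence also comes last in the effectiveness list and is not one of the three bolded outcomes, which limits what is at stake.

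**Conclusion.** The point holds in this form: as written, 6.2(9), read with 7.1 and the flow chart, counts complications present but undetected at entry as post-treatment events. The adverse event definition is a sound, inclusive safety rule. The fault lies in its unmodified reuse for an effectiveness incidence.

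The size cannot be derived from the protocol. Under assumed undetected prevalence of 0.5% to 2% and true incidence of 1% to 5%, between 9% and 67% of recorded cases would be baseline cases. The effect is nil if nothing is undetected at baseline, and no spurious difference between cohorts arises if the undetected prevalence is equal across them. A reader might infer that the integrated cohort would be penalised because sicker patients receive combined therapy. That is conjecture: the protocol does not show which cohort is sicker, and the bias could run either way.

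The change is worth making before enrolment is complete, because it is cheap and corrects a stated rule.

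**What to change.** 1. In the flow chart, add a baseline entry, completed before the first dose, to the complication row and the severe or critical illness row. Make clear how the baseline column relates to Visit 1 D0.
2. In 6.2(9), define the outcome as new-onset complications among patients free of that complication at baseline, using the time of occurrence that 7.2 already requires.
3. State that a complication shown by a sample or image taken at or before the first dose is baseline, whatever the date of the result.
4. Leave the adverse event definition in 7.1 unchanged for safety reporting.
5. Reconcile what the Program Summary, 3.2, 5.2 and 6.3 say about liver and kidney function tests at D0.

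The cost is one extra baseline field, a few lines of wording and a slightly smaller denominator. The change is only a partial cure: a complication with no baseline test can still go unseen at entry, and its classification will rest on the recorded onset.
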